Minimization of risks: To ensure medical readiness to begin physical activity, participants will complete a physical activity readiness questionnaire (PAR-Q). The PAR-Q assesses for the following medical conditions: heart problems, chest pains, faintness or dizzy spells, high blood pressure, bone, or joint problems such as arthritis that has been or could be aggravated by exercise, prescription medication use, and other medical reasons why exercise would not be advisable. Participants endorsing yes to any items on the PAR-Q (experience of heart problems, frequent chest pains, faintness or dizziness, bone or joint problems, on prescription medications for blood pressure or a heart condition) will be excluded from the study.

We also will monitor any major musculoskeletal problems that develop during the intervention (e.g., broken bones) using a medical events questionnaire at 3 months and determine whether these appear related to our study. Participants who develop musculoskeletal problems or other health problems that may affect safe participation will be instructed to stop exercising until the problem resolves and their physician approves resumption of physical activity.

Participation is fully voluntary, and we will ask participants to report any problems to the study researchers.

2. Risk of wearable devices: There is also the possibility of minor skin irritation associated with wearable devices.

Minimization of risk: We will recommend taking the device off occasionally, not wearing it too tightly, and keeping it clean and dry. If participants experience skin irritation, we will suggest that they contact a member of the study team to discuss the issue and determine whether they would like to continue participating in the study.

3. Risk of using a phone while driving: It is dangerous to pay attention to a cellular phone while driving, walking, or doing any activity that requires attention.

Minimization of risk: We will strongly recommend that participants exercise good judgment on this while participating in this study and will ask that they not open the application or view any notifications or messages while they are driving.

4. Risk of CGM: There is a small risk that the adhesive used to attach the sensor to the arm will cause skin irritation.

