5.2 EXCLUSION CRITERIA

An individual who meets any of the following criteria will be excluded from participation in this study:

- Lost more than 10 pounds in the last 6 months
- History of weight loss surgery
- Currently participating in another physical activity or weight loss program or research study that may interfere with participation in this study
- Currently meeting exercise recommendations of 150 minutes per week of moderate-to-vigorous physical activity
- Currently pregnant, pregnant within the past 6 months, or planning to become pregnant within the next 4 months
- Planning to relocate in the next 4 months
- Cannot attend weekly visits at the UNC Weight Research Program clinic
- Pre-existing medical condition(s) that preclude adherence to an unsupervised exercise program, as determined by items endorsed on the PAR-Q (Physical Activity Readiness Questionnaire)
- Treatment of diabetes with insulin or oral medications
- Report taking prescription or over the counter medication with a known impact on metabolism or weight
- Current treatment for cancer
- History of clinically diagnosed eating disorder
- Diagnosis of schizophrenia or bipolar disorder
- Hospitalization for a psychiatric diagnosis within the last year
- Report a past diagnosis of or current symptoms of alcohol or substance dependence
- Unwilling or unable to wear the CGM device continuously for the duration of the study
- On dialysis
- Have an implanted medical device such as a pacemaker

All participants will be required to obtain consent from their primary care provider in order to participate.

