14. In a typical week, how many days do you do any physical activity or exercise of at least moderate intensity, such as brisk walking, bicycling at a regular pace, and swimming at a regular pace?
 None
 1 day per week

- 2 days per week
- 3 days per week
- 4 days per week
- 5 days per week
- 6 days per week
- 7 days per week

15. On the days that you do any physical activity or exercise of at least moderate intensity, how long do you typically do these activities?

16. Have you ever had or are you currently receiving treatment for any of the following?

a. Pre-Diabetes or Diabetes Yes No (INELIGIBLE)

If yes, how is it controlled? _____

Diet and exercise

Prescription medication (INELIGIBLE)

Insulin (INELIGIBLE)

Other (describe)

b. Hospitalization in the past year for depression or other psychiatric disorder Yes (INELIGIBLE) No

c. Schizophrenia or bipolar disorder? Yes (INELIGIBLE) No

d. Alcohol or substance abuse? Yes (INELIGIBLE) No

e. Anorexia or bulimia? Yes (INELIGIBLE) No

f. Cancer Yes (Current treatment = INELIGIBLE) No

break

1. Has a doctor ever said that you have a heart condition AND that you should only do physical activity recommended by a doctor? No Yes (INELIGIBLE)
2. Do you feel pain in your chest when you do physical activity? No Yes (INELIGIBLE)
3. In the past month, have you had chest pain when you WERE NOT doing physical activity? No Yes (INELIGIBLE)

4. Do you ever lose your balance because of dizziness or do you ever lose consciousness?
 No Yes (INELIGIBLE)

5. Do you have a bone or joint problem that could be made worse by a change in your physical activity?
 No Yes

6. Is your doctor currently prescribing drugs for your blood pressure, cholesterol, or a heart condition?
 No Yes

7. Do you know of any other reason why you should NOT do physical activity?

NO YES

8. Are you currently on dialysis?

NO YES (INELIGIBLE)

9. Do you have an implanted medical device (for example, a pacemaker)?

NO YES (INELIGIBLE)

If yes, please describe: _____

Break

25. Are you taking any prescription medications?

NO Yes

26. Are you taking any non-prescription over the counter dietary supplements?

NO Yes

Break

27. Do you have access to the Internet at home? Yes No (INELIGIBLE)

If yes, How do you access the Internet at home (Check all that apply)?

- Computer (desktop or laptop)
- Smartphone or cell phone
- Tablet

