12.3 TELEPHONE SCREENER

1. When you filled out the online screening questions, you reported that your weight is _____ lbs. and your height is _____. Is this accurate to the best of your knowledge?

BMI = _____ **MUST BE 25 – 40;**

If BMI calc on edges of eligibility (25-27 or 38-40), “If you are eligible after we finish these screening questions and you decide you would like to participate, we will confirm your height and weight at your first study visit at our center.”

2. *If Yes to Cancer question 17.*

In the online screener, you reported having been diagnosed with cancer in the past. Can you tell me when that was? Are you currently being treated for Cancer? (If current treatment, INELIGIBLE)

3. *If yes to Question 23 on web screen: Do you know of any other reason why you should not do physical activity?*

In the online screener, you answered yes to the question “Do you know of any other reason why you should not do physical activity?” Can you explain? (INELIGIBLE if they can’t do activity akin to walking and progress to 150 minutes of Moderate to Vigorous PA per week over time)

4. *If Yes to Question 25 on web screen: Are you taking any other prescription medications?*

You reported that you are taking prescription medications. Can you tell me the names of them? (Also ask what it is used to treat)

If Yes, specify: _____

(NOTE: look for meds with known effects on appetite or weight, oral steroids, diabetes meds-- INELIGIBLE)

6. *If Yes to Question 26 on web screen: Are you taking any non-prescription over the counter dietary supplements?*

You reported that you are taking non-prescription over the counter dietary supplements. Can you tell me the names of them?

If yes, specify: _____

If other than vitamin/mineral supplement: Would you be willing to stop taking this supplement during the study period? **NO** (INELIGIBLE) Yes

7. Are you currently participating in any other weight loss or physical activity program?

8. Are you currently a member of any other research studies?

NO Yes

If yes, describe _____
(If other study would interfere with following study protocol, INELIGIBLE)

Thanks for taking the time to answer my questions.

You submitted the following contact information on the website (*read their info. from the web report*).
Has any of this changed? [*If so, note below*].

Name: _____

Street Address: _____

City: _____ State: _____ Zip Code: _____

Home Phone: _____ Work Phone: _____ Cell Phone: _____

Email Address: _____

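### Section 2.3.1 excludes anyone who answers yes to any PAR-Q item, but the screeners do not apply this to bone or joint problems or to blood-pressure and heart drugs, and apply it only conditionally to the last item

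*Combined protocol and SAP*

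**What the plan says.** Four places in the combined protocol and SAP bear on this.

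- **Section 2.3.1, minimization of risks for physical activity.** The rule is categorical: "Participants endorsing yes to any items on the PAR-Q" are out. A parenthesis names five conditions: heart problems, chest pains, faintness or dizziness, and then "bone or joint problems, on prescription medications for blood pressure or a heart condition) will be excluded from the study".
- **Section 5.2, and exclusion criterion 7 in the section 12 appendix.** These exclude medical conditions that rule out exercising without supervision, "as determined by items endorsed on the PAR-Q (Physical Activity Readiness Questionnaire". Neither says that any single yes is enough.
- **Section 12.3, Online Screener.** Seven physical-activity readiness items are printed as numbers 1 to 7. Items 1 to 4 are marked ineligible on a yes. Items 5, 6 and 7 offer only yes and no.
- **Section 12.3, Telephone Screener.** For prescription drugs, staff collect the names and are told "Also ask what it is used to treat". The exclusion note then reads "look for meds with known effects on appetite or weight, oral steroids, diabetes meds-- INELIGIBLE". For online item 7, a yes excludes only a person who cannot "do activity akin to walking and progress to 150 minutes of Moderate to Vigorous PA per week over time".

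**The concern.** The risk section lists joint injury, abnormal blood pressure, heart rhythm disorders and, very rarely, heart attack, stroke or death among the risks of increasing activity. It presents the PAR-Q exclusion as the screening safeguard. The two named conditions that the forms do not enforce concern joints, and drugs for blood pressure or the heart, so they bear directly on those risks.

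If staff work from the forms, people whom section 2.3.1 excludes can pass screening and enter the activity progression of section 6.1.1. If staff work from section 2.3.1, the same people are screened out. Two consequences follow.

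- **Who is enrolled.** The planned sample is 20, so each participant is 1/20 = 5% of it. If section 2.3.1 governs, enrolling such a person is also noncompliance with the protocol, which section 10.1.10 defines as a deviation.
- **Recruitment feasibility.** Section 2.1 says the study will establish this. A screening yield is hard to interpret when the documents hold more than one eligibility rule.

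**Working it through.** No formula applies to the main point, so I set the texts side by side. The inputs are the any-yes rule in section 2.3.1 and, for each of the seven items, the online mark and any telephone follow-up in section 12.3.

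| Online item | Online mark on yes | Telephone follow-up | Agrees with section 2.3.1? |
|---|---|---|---|
| 1. Heart condition with doctor's restriction | Ineligible | Not needed | Yes |
| 2. Chest pain with activity | Ineligible | Not needed | Yes |
| 3. Chest pain without activity | Ineligible | Not needed | Yes |
| 4. Dizziness or loss of consciousness | Ineligible | Not needed | Yes |
| 5. "Do you have a bone or joint problem that could be made worse by a change in your physical activity" | None | None shown | No |
| 6. "Is your doctor currently prescribing drugs for your blood pressure, cholesterol, or a heart condition" | None | Drug names and uses collected; these drugs not on the exclusion note | No |
| 7. Any other reason | None | Excludes only if walking-type activity and progression are not possible | Only conditionally |

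**Tally by item.** 4 of 7 agree and 7 − 4 = 3 depart.

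**Tally by named condition.** Of the five in the parenthesis, heart problems, chest pains, and faintness or dizziness are enforced online (3). Bone or joint problems and blood-pressure or heart medication are not (2).

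**A further mismatch.** Item 6 also covers cholesterol drugs, which the parenthesis does not name. Under the any-item rule, a yes given only because of a cholesterol drug would exclude.

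**Are these seven items the PAR-Q?** The screener does not label them so, but they closely track the conditions that section 2.3.1 says the PAR-Q assesses, including its final category of other medical reasons. No separate PAR-Q appears in the schedule text or among the assessments in section 8.1.

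**Could marks have been lost in reading the PDF?** Unlikely. The marks survive on items 1 to 4, 8 and 9 of the same list. The telephone follow-up to item 7 would also have no purpose if a yes online already excluded.

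**The activity progression.** Section 6.1.1 starts the least active at 10 min/day and adds 5 minutes after each week in which the goal is met, up to 60 min/day. The goal in week k is 10 + 5(k − 1). Setting this equal to 60 gives k = 11, so a participant who meets every weekly goal reaches the maximum in week 11 of 12.

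**The case against.** The strongest objection is that a missing mark on a form is not an enrolment rule. The screeners leave other firm criteria unmarked, such as age, weekly activity minutes and lack of a data plan. Section 8.1 has staff confirm eligibility at each point, and the project coordinator reviews the answers before deciding. Every participant also needs consent from a primary care provider. This has some force: it shows that wrongful enrolment is possible, not certain. It does not remove the contradiction. Marking items 1 to 4 and leaving 5 to 7 blank in one list looks deliberate, and the telephone rule for item 7 conflicts directly with an any-item rule. Neither the coordinator review nor the provider consent is stated, in the text available, to apply the any-yes rule. The physician's consent form itself is not in that text, so what it covers cannot be checked.

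Other points are fair but limited.

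- A separate PAR-Q form may exist. The counts of 4 and 3 assume that the seven online items are the PAR-Q. If there is another form, the documents do not say when it is given or how it is scored.
- The telephone numbering jumps from 4 to 6, so a bone or joint question could be missing. Items 6 and 7 would still conflict.
- Section 5.2 can be read as agreeing with section 2.3.1, if endorsing an item is itself what determines exclusion. The screeners would then depart from both.
- Item 7 is a softer departure, because the parenthesis does not name it and its telephone rule is close to section 5.2. The clear core is items 5 and 6.

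**Conclusion.** The concern holds. Section 2.3.1 and the screeners state different exclusion rules: 3 of 7 items depart from the any-yes rule (two outright, one conditionally), including 2 of the 5 named conditions. The wording of section 5.2 and the appendix leaves open which rule was meant. The counts rest on treating the seven online items as the PAR-Q, which their content supports.

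This is a contradiction in a stated safety exclusion, so it should be corrected. It affects who can be enrolled and how screening yield is read. It changes no endpoint, estimate or test. The documents do not allow an estimate of how many candidates are affected.

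**What to change.** Reconcile section 2.3.1, section 5.2, appendix exclusion criterion 7 and both screeners into one item-by-item rule.

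- For each of the seven items, state whether a yes excludes outright, excludes under a stated condition, or goes to a named reviewer such as the project coordinator or the primary care provider. Use the same wording everywhere.
- Match the online marks and telephone follow-ups to that rule. Item 5 needs a stated consequence, and the telephone drug question needs an instruction for the drugs in item 6.
- If a separate PAR-Q form is used, say when it is completed and how it is scored.
- Record PAR-Q screen-outs by item. Section 8.1 already keeps reasons for ineligibility and the telephone form has a reason field, so only the item detail is new.

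Which rule is right is a decision for the investigators and the IRB. The cost is protocol and screener wording and REDCap form logic, with no added visits or procedures. If the any-yes rule is kept and enforced, fewer candidates may pass screening.

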2.3.2 KNOWN POTENTIAL BENEFITS

This study may help researchers understand the acceptability of CGM in a pre-diabetes and T2D population and determine if incorporating daily monitoring of BG within the context of a behavioral weight loss intervention promotes self-regulation and adherence to lifestyle changes necessary for weight loss. Given the widespread prevalence of T2D and obesity, this study could inform larger trials that could lead to clinical recommendations.

The benefits of participation in a short-term program that includes weighing, increasing physical activity, and dietary changes may include weight loss and short-term improvements in activity and eating. Increased physical activity and healthier eating can also lead to other improvements in health, such as improved cardiovascular outcomes. Better glucose control (over time) could result in fewer vascular complications.

2.3.3 ASSESSMENT OF POTENTIAL RISKS AND BENEFITS

The occurrence of an adverse event (AE) or serious adverse event (SAE) may come to the attention of study personnel during weekly individual coaching sessions.

All AEs, not otherwise precluded per the protocol, will be captured on the appropriate adverse events form.

A Medical Events questionnaire will be administered at the 12-week follow up assessment. To capture any adverse events not reported during the individual coaching sessions.

3 OBJECTIVES AND ENDPOINTS

OBJECTIVES	ENDPOINTS	JUSTIFICATION FOR ENDPOINTS
Primary		
Change in weight (kg).	Weight change at 12 weeks	The primary goal of the intervention is weight loss, thus change in weight is appropriate
Secondary		
1. Change in Body Mass Index (BMI) 2. Change in HbA1c from baseline to 12 weeks. 3. Change in compliance behavior and efforts at diabetes self-control from baseline to 12 weeks as measured by the Diabetes Locus of Control Scale 4. Change in Diabetes-related Quality of Life from baseline to 12 weeks as measured by the Diabetes Obstacles Questionnaire.	Change in measures at 12 weeks	1. BMI is commonly used to assess level of overweight. 2. Change in HbA1c is a valuable diagnostic clinical measure for glucose management over the past 3 months and is responsive to changes in diet, physical activity and weight. 3. Change in compliance behavior and efforts at diabetes self-control may moderate weight loss and HbA1c outcomes. 4. Change in obstacles to adhere to diabetes treatment recommendations may moderate weight loss and HbA1c outcomes.
Tertiary/Exploratory		
To examine the feasibility of using Continuous Glucose Monitoring in overweight individuals as an indicator of response to diet and physical activity behavior modification to promote weight loss. Acceptability and effectiveness of the Traffic Light diet Red food monitoring	1. Responses to Glucose Monitoring System Satisfaction Survey and Technology Acceptance Model-Continuous Glucose Monitoring at 12 weeks. 2. Adherence to Blood Glucose monitoring 1. Adherence to Traffic Light diet monitoring across the 12-week intervention	

OBJECTIVES	ENDPOINTS	JUSTIFICATION FOR ENDPOINTS
	Association between adherence to Red food goals and change in weight	

4 STUDY DESIGN

4.1 OVERALL DESIGN

This project will test a weight loss intervention delivered through a mobile app for use in non-medication treated type 2 diabetics and pre-diabetics. The app is designed to integrate self-monitoring data from wireless scales and physical activity trackers, allow self-monitoring of foods through a Traffic Light diet approach, serve as a portal for feedback on behaviors and outcomes, and provide a platform for behavioral lessons. We will use the app coupled with in-person support to inform future versions.

We propose a single arm pilot trial testing the feasibility of a behavioral weight loss intervention for adults with type 2 diabetes or prediabetes. Participants will be instructed to decrease intake of Red foods, weigh daily, monitor BG using a CGM system, and gradually increase minutes of physical activity. This 12-week intervention is aimed at promoting improvements in diet quality consistent with recommendations for T2D, a decrease in energy intake, an increase in energy expenditure, and modest weight loss with a goal of improving glycemic control. Participants will meet weekly with a lifestyle counselor (interventionist) to review data on all behaviors, weight, and BG. The session will include feedback on progress, discussion of core content, problem solving and goal setting.

Participants will be given activity trackers (Fitbit Inspire) and wireless digital scales (Withings) to use for the duration of the study. Dietary behaviors will be monitored using an app that our research team has developed to track foods using the Traffic Light system. Assessments will occur at baseline and 12-weeks. Weight will be collected in the clinic on calibrated digital scales (Tanita) during in-person counseling sessions. Adherence measures will include self-monitoring and activity tracking, attendance at individual sessions and achievement of weekly diet and activity goals.

4.2 SCIENTIFIC RATIONALE FOR STUDY DESIGN

This study is specifically designed to test the feasibility of conducting the intervention as well as to collect preliminary data to be used to develop and propose a larger randomized controlled trial. The proposed research is funded under a pilot/feasibility research program with limited funding. Therefore, a single group design with a limited number of participants is acceptable.

4.3 JUSTIFICATION FOR INTERVENTION

Weight loss is recommended for individuals with overweight or obesity and impaired glucose. Behavior change interventions are the first line of treatment and are effective at reducing weight and improving glycemic control. Weight loss of 5-10% is associated with clinical improvements.

Digital weight loss interventions that integrate behavior change techniques and supports including diet, physical activity, and weight self-monitoring have been shown to be effective for weight loss in adults.

Expert support is also a key component of behavioral weight loss interventions. In this study, we will use human counseling rather than automated feedback in order to best gather feedback and impressions on the feasibility of implementing this intervention given the exploratory nature of using the Traffic Light approach for diet monitoring and CGM for this non-insulin dependent population.

.4 END OF STUDY DEFINITION

The end of the study is defined as completion of the 12-week follow-up assessment shown in the Schedule of Activities (SoA), **Section 1.3**.

5 STUDY POPULATION

5.1 INCLUSION CRITERIA

In order to be eligible to participate in this study, an individual must meet all of the following criteria:

- Currently age 20-65 years
- Diagnosed with type 2 diabetes or pre-diabetes
- Poor glycemic control ($\text{HbA1c} \geq 5.7\%$)
- BMI 25-40 kg/m²
- Own an iPhone with a data and text messaging plan
- Have home Wi-Fi access
- Have the ability to read, write, and speak English
- Not meeting the American College of Sports Medicine recommendation of 150 minutes of Moderate to Vigorous Physical Activity each week
- Ability to attend weekly visits at the UNC Weight Research Program clinic
- Can obtain primary care provider consent that appropriation is appropriate

